6.1. Objectives and Endpoints of the Efficacy Study Part (Arms 1-3)

6.1.1. Primary Objective and Endpoints

1. To measure the effect of treatment with E4 15 mg or E4 20 mg E4 compared to placebo on the frequency and severity of moderate to severe VMS in postmenopausal women at 4 and 12 weeks

Co-primary efficacy endpoints for primary objective #1

- 1.1. Mean change in weekly frequency of moderate to severe VMS from baseline to week 4
- 1.2. Mean change in weekly frequency of moderate to severe VMS from baseline to week 12
- 1.3. Mean change in severity of moderate to severe VMS from baseline to week 4
- 1.4. Mean change in severity of moderate to severe VMS from baseline to week 12

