8.1.1. Justification of Sample Size

Efficacy Study part: based on results observed for the E4 15 mg dose in the Phase 2 study, a sample size of ~200 subjects per arm provides a power of at least 80% to simultaneously achieve a superiority (upper bound of a 95% 2-sided confidence interval [CI] lower than zero) over placebo for the four co-primary endpoints together. This sample size accounts for a dropout rate during the first 12 weeks of the study of 35% and 20% for non-hysterectomized and hysterectomized women, respectively.

It is planned to enroll approximately 100 hysterectomized and 100 non-hysterectomized subjects per treatment arm.

Safety Study part: the target number of ~400 subjects has been selected to fulfill the requirement stated in International council for harmonization of technical requirements for pharmaceuticals for human use (ICH) E1 guideline (CPMP/ICH/375/95) regarding number of subjects exposed to the drug for safety assessments.

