8.2. Inclusion and Exclusion Criteria

8.2.1. Criteria for Inclusion

Subjects will be allocated to treatment if they meet all of the following inclusion criteria:

1. Signed and dated written informed consent form and any required privacy authorization prior to the initiation of any trial procedure, after the nature of the trial has been explained according to local regulatory requirements;
2. Females, ≥ 40 up to ≤ 65 years of age at randomization/treatment allocation;
3. For hysterectomized subjects: documented hysterectomy must have occurred at least 6 weeks prior to the start of screening. Hysterectomy can be total or subtotal (i.e., cervix was not removed);
4. For non-hysterectomized subjects: uterus with bi-layer endometrial thickness ≤ 4 mm on TVUS;
5. For non-hysterectomized subjects: endometrial biopsy taken during screening that reveals no abnormal result, i.e., presence of hyperplasia (simple or complex, with or without atypia), presence of carcinoma, and presence of disordered proliferative endometrium findings. The screening biopsy should have sufficient endometrial tissue for diagnosis. Biopsies without tissue or with insufficient tissue may be repeated once;
6. Seeking treatment for relief of VMS associated with menopause;
 - a. For the Efficacy Study part: at least 7 moderate to severe bothersome VMS per day or at least 50 moderate to severe bothersome VMS per week in the last 7 consecutive days during the Screening period¹²;
 - b. For the Safety Study part: at least 1 moderate to severe VMS per week;
7. Body mass index ≥ 18.0 kg/m² up to ≤ 38.0 kg/m²;
8. A mammogram that shows no sign of significant disease performed during screening or within 9 months prior to the start of screening¹³;
9. Postmenopausal status defined as any of the following:
 - a. For non-hysterectomized subjects:
 - At least 12 months of spontaneous amenorrhea with serum follicle stimulating hormone (FSH) >40 mIU/mL (value obtained after washout of estrogen/progestin containing drugs, see exclusion criteria 18 and 20);
 - or at least 6 months of spontaneous amenorrhea with serum FSH >40 mIU /mL and E2 <20 pg/mL (value obtained after washout of estrogen/progestin containing drugs, see exclusion criteria 18 and 20);
 - or at least 6 weeks postsurgical bilateral oophorectomy³;

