12.4. Primary Efficacy Variables

The weekly frequency of moderate to severe VMS at baseline, week 4 and week 12, respectively, is defined as the total number (sum) of all recorded moderate to severe VMS experienced during the last 7 consecutive days during the Screening period, days 22 to 28 (week 4) and days 78 to 84 (week 12), respectively.

The mean severity score of VMS is defined as the arithmetic mean of the daily severity score values of VMS (moderate or severe) observed from days -7 to -1 at baseline and the arithmetic mean of the daily severity score values of VMS (mild, moderate or severe) observed during the days 22 to 28 and days 78 to 84 for week 4 and week 12 respectively.

At baseline, the daily severity score is computed as $[(2 \times \text{number of moderate VMS}) + (3 \times \text{number of severe VMS})] / (\text{total number of moderate + severe VMS})$ if at least one moderate to severe VMS was recorded during the day. In case of documented absence of moderate to severe VMS during the day, the daily severity will be set to zero.

Post-baseline (days 22 to 28 [Week 4] and days 78 to 84 [Week 12]), the daily severity score is computed as $[(1 \times \text{number of mild VMS}) + (2 \times \text{number of moderate VMS}) + (3 \times \text{number of severe VMS})] / (\text{total number of mild + moderate + severe VMS})$ if at least one mild to severe VMS was recorded during the day. In case of documented absence of VMS during the day, the daily severity will be set to zero.

The daily severity score as defined above will also be recomputed for post baseline weeks as $[(2 \times \text{number of moderate VMS}) + (3 \times \text{number of severe VMS})] / (\text{total number of moderate + severe VMS})$ if at least one moderate or severe VMS is recorded during the day.

The primary efficacy variables will be expressed as the changes from baseline computed as the differences between the estimated values at week 4 or 12 and the baseline values.

The analysis including the mild VMS will be used for submission to the FDA, the analysis without the mild VMS will be used for submission to the EMA.

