12.5. Analysis of Primary Efficacy Variables

All statistical tests will be supported by presenting estimates and 95% CIs for the respective treatment effects (difference to placebo). These estimates and CIs will be based on the respective statistical models used for the analysis. Since all analyses of the efficacy variables are not exploratory in nature, adjustment for multiplicity will be performed (Dunnet adjustment for the comparison of each active dose versus placebo).

The primary efficacy comparison will test the following hypotheses for each treatment arm:

- H0: The average change from baseline in the primary efficacy endpoint in the treatment arm is greater (less pronounced) or equal to the average change from baseline in the placebo arm
- H1: The average change from baseline in the primary efficacy endpoint in the treatment arm is lower (more pronounced) to the average change from baseline in the placebo arm

The two dose groups of E4 will be compared to placebo regarding the four co-primary endpoints.

A comparison between treatment arms of the change from baseline at week 1 to week 12 in the weekly frequency of moderate to severe VMS and of the change from baseline in the weekly mean severity of moderate to severe VMS will be made by using Mixed-effect Models for Repeated Measures (MMRM). The MMRM models will include treatment, week, treatment by week interaction and pooled trial centers as fixed effects and baseline as a covariate. If the pooled center effect included in the model is significant, a treatment by center interaction will be included in the model. Treatment effects will be assessed at week 4 and 12 using two separate MMRM models (one on weekly frequency and another on weekly mean severity).

The primary analysis will use the data from the ITT population. Since an MMRM model is used, missing data imputation is not necessary. Additional sensitivity analyses will be implemented in order to assess the robustness of the results. These may include sensitivity with respect to:

- An imputation of missing data (last observation carried forward [LOCF] or other)
- The modelling strategy [analysis of covariance (ANCOVA) instead of MMRM]
- Confounders (for example ethnicity, hysterectomized status)
- Populations studied (mITT, PP)
- Any combination of the above

In addition, all primary efficacy variables will be tabulated at baseline and at each post-baseline time point.

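### The severity MMRM is valid, but it leaves out baseline VMS frequency, a modestly prognostic covariate already collected; adding it before unblinding is a small efficiency gain at almost no cost.

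*Protocol*

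**What the plan says.** Section 12.5 assesses treatment effects at Weeks 4 and 12 "using two separate MMRM models (one on weekly frequency and another on weekly mean severity". Both models carry treatment, week, their interaction, and "pooled trial centers as fixed effects and baseline as a covariate". The Synopsis repeats this. Neither place says which baseline is meant. With one model per outcome, the natural reading is each outcome's own baseline. Other covariates appear only in a list of optional sensitivity analyses, as confounders such as ethnicity and hysterectomy status; baseline frequency is not named there.

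Section 12.4 defines weekly severity as the mean of seven daily scores. For the post-baseline score that counts mild VMS (for the FDA): "In case of documented absence of VMS during the day, the daily severity will be set to zero". For the recomputed score without mild VMS (for the EMA), the formula applies "if at least one moderate or severe VMS is recorded during the day", and the zero rule is not restated.

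Baseline weekly frequency is the count "experienced during the last 7 consecutive days during the Screening period". Entry to the Efficacy Study part requires "at least 7 moderate to severe bothersome VMS per day or at least 50 moderate to severe bothersome VMS per week" (8.2.1). Severity at Weeks 4 and 12 makes up two of the four co-primary endpoints, the last being "Mean change in severity of moderate to severe VMS from baseline to week 12" (6.1.1).

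**The concern.** A weekly severity score that averages in zeros is part intensity and part a count of symptom-free days. At baseline the entry floor makes VMS-free days rare, so baseline severity lies close to the 2-to-3 range and says little about how near a woman is to having such days. Baseline frequency says more, and the plan already derives it.

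The sample size rests on winning all four co-primary endpoints together, each by the criterion "upper bound of a 95% 2-sided confidence interval [CI] lower than zero" (8.1.1). Unexplained variance in the severity model therefore lowers power on two of the four tests, and through them the joint power. The question is by how much.

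**Working it through.** **The plan's own figures.** Completers at Week 12: 300 × 0.65 + 300 × 0.80 = 435, as stated in 8.1, or 145 per arm. The stated power of at least 80% cannot be reproduced, because 8.1.1 gives no effect size, SD or correlation between endpoints.

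**Mechanism.** Section 7.1.3.3 quotes Phase 2 VMS reductions of 65% (placebo) and 84% (E4 15 mg). Take Poisson daily counts and starting rates of 55 and 150 per week; both rates and the Poisson form are assumptions. The chance of a VMS-free day is exp(−daily rate):
- 65% reduction: 55 × 0.35 / 7 = 2.75 per day gives 6%; 150 × 0.35 / 7 = 7.5 per day gives under 0.1%.
- 84% reduction: 55 × 0.16 / 7 = 1.26 per day gives 28%; 150 × 0.16 / 7 = 3.43 per day gives 3%.

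So baseline frequency matters for zero days, mainly when the response is large. Differences in response between women dilute this.

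**From correlation to power.** Let r be the partial correlation between baseline frequency and on-treatment severity, given the other model terms. Adding the covariate multiplies residual variance by 1 − r² and the standard error by √(1 − r²), and it is worth n / (1 − r²) completers per arm. Power is for one severity test that stands at 80% when r = 0, at two-sided 0.05 and at the large-sample Dunnett level for two doses against placebo (critical value 2.212, 0.0270 per comparison):

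| r | Variance × | SE × | Power, 0.05 | Power, Dunnett | Equivalent n per arm |
|---|---|---|---|---|---|
| 0 | 1.000 | 1.000 | 80.0% | 80.0% | 145 |
| 0.1 | 0.990 | 0.995 | 80.4% | 80.4% | 146.5 |
| 0.2 | 0.960 | 0.980 | 81.6% | 81.7% | 151.0 |
| 0.3 | 0.910 | 0.954 | 83.6% | 83.9% | 159.3 |

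**What r is plausible.** The documents give none, so it was simulated at Week 12. Inputs were baseline of at least 50 per week, the 65% and 84% reductions, and daily scores as in 12.4. Assumed spreads were a baseline SD of about 20–68 per week and a between-woman SD of log response of 0.6–1.5.
- *With mild VMS.* Overdispersed counts: ratio of residual variance without to with log baseline frequency 1.013–1.079, a cut of 1 − 1/1.013 = 1.3% to 1 − 1/1.079 = 7.3%. The mid-case is 1.041, a cut of 3.9%. Poisson counts: r about 0.10–0.27, a cut (r²) of 1–7%.
- *Without mild VMS, zero on days with no moderate or severe VMS.* Ratios from about 1.01 up to 1.15, a cut of about 1–13%; mid-case 1.053, a cut of 5.0%.
- *Without mild VMS, such days left out.* r about 0, so no gain.
- *Frequency model with baseline severity added.* Ratio 1.000, so no change is needed there.

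The upper ends are not limits. A further set of runs with similar spreads reached 1.13 and 1.19 for the two scores, while its mid-cases (1.04–1.06 and 1.05–1.07) stayed close to those above.

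**Mid-case, score with mild VMS.** 145 × 0.041 = 5.9, about 6 women per arm. This is close to the r = 0.2 row: standard error about 2% smaller, one test from 80% to about 81.6%. If four independent tests share the 80%, each needs 0.80^(1/4) = 94.6%; r = 0.2 lifts a severity test to 95.3%. Joint power becomes 0.80 × (0.953 / 0.946)² ≈ 81%.

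**The case against.** The strongest reply is that nothing is wrong. A pre-specified MMRM with the outcome's own baseline gives a valid randomized comparison, and its error rate already allows for chance imbalance in baseline frequency. That stands in full.

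It is also fair that the gain is small and rests on spreads that are not in the documents. On-treatment zero days follow individual response more than starting frequency, and the entry floor narrows the baseline range. Only Week 12 was simulated, as a single-time-point regression rather than the full repeated-measures model; Week 4 is inferred. These points limit the size of the claim. They do not remove it, since the gain was positive in every scenario in which symptom-free days score zero.

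For the score without mild VMS, the zero rule is uncertain. Section 12.6 has a zero rule for days without moderate to severe VMS, but under the secondary variables, and the matching Synopsis sentence refers to absence of any VMS. Zero is a reasonable reading, not a settled one.

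The Efficacy Study Part SAP (version 3.0, cited in section 1 of the Safety Study part SAP) was not available. It may already name the covariates. The open-ended confounder list in 12.5 would also allow baseline frequency, but only as an optional sensitivity analysis.

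**Conclusion.** The point holds as an efficiency gain, not as the correction of an error. As written, the severity MMRM leaves out one modestly prognostic covariate that is already in the data. For the score with mild VMS, adding it is worth about 1–7% of residual variance, with a mid-case of about 4%. For the score without mild VMS it is worth about 1–13%, conditional on the zero rule. All of these figures depend on the assumed spreads.

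Three stronger readings are not supported:
- *That the severity tests are biased or invalid.* They are neither; the omission affects precision only.
- *That the severity endpoints depend strongly on baseline frequency, or are materially underpowered for lack of it.* The mid-case moves one test near 80% by 1–2 points and joint power by about one. The 8.1.1 power statement cannot be tested from what is given.
- *That about 21 women per arm are lost.* That figure (145 × 0.143) comes from an extreme scenario for the score without mild VMS and needs a zero rule that 12.4 does not state for it.

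**What to change.** Before unblinding, state in 12.5 and the Synopsis which baseline enters each model. For the severity MMRM, name two: baseline mean severity, and baseline weekly frequency of moderate to severe VMS on the log scale (the entry floor keeps the log defined). Use the same pair in the ANCOVA sensitivity version. Leave the frequency model as it is. Align the Efficacy Study Part SAP if it does not already say this. The sponsor's Phase 2 data could be used to estimate the partial correlation and hence the expected gain.

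The cost is a sentence in each document and one degree of freedom, with no new data or visits. It must be settled before unblinding, since a covariate added afterwards would look data-driven.

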7.2. Study and Treatment Assignment

Assignment into any of the study parts (i.e. Efficacy and Safety) and treatment subgroups (15 mg, 20 mg and placebo) will be done by the Interactive Web Response System (IWRS) system (i.e cannot be done by site staff). This assignment will take into account the modified MENQOL score, frequency and severity of hot flashes, hysterectomized vs. non-hysterectomized status, and availability of places in each study part/subgroup.

Efficacy Study part

Subjects eligible for participation in the Efficacy Study part will be randomly allocated to one of the three treatment arms [E4 15 mg (Arm 1), E4 20 mg (Arm 2) or placebo (Arm 3)] in a 1:1:1 ratio using a computer-generated randomization schedule.

Safety Study part

Subjects eligible for participation in the Safety Study part will all be allocated to treatment with E4 20 mg (Arm 4).

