7.3. Randomization

A randomization schedule will be generated within the Biometrics Department of the designated CRO by a statistician not involved in the trial. The randomization schedule will be generated by means of the PLAN procedure of SAS®. The computer program uses the method of randomly permuted blocks. The block size will not be revealed before unblinding.

An Interactive Web Response System (IWRS) will be used for the randomization procedure. A subject ready for randomization will be entered in the IWRS. The respective next subject eligible for randomization will receive the lowest available randomization number at the trial center. A randomization confirmation including treatment assignment (i.e., kit number), date and time will be sent to the center, to the designated project managers or designee of the CRO and to the Sponsor's project manager.

The randomization schedule and the complete generation procedure will be filed at a secure place by the designated CRO until the trial database is unblinded. A copy of the list will be sent to the Pharmaceutical Supply for the purpose of assigning the kits to the subjects.

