8. SUBJECT SELECTION AND DISCONTINUATION/WITHDRAWAL OF SUBJECTS

8.1. Source and Number

This will be a multicenter trial performed in multiple study sites in the United States of America and Canada. Subjects will be recruited by the investigator from his/her patients or will be recruited by recruitment campaigns. Subjects must seek treatment for the relief of menopausal symptoms, or subject may already be treated for menopausal symptoms and willing to discontinue their current treatment.

All investigators must keep a record of subjects who were considered for enrollment and were consented, but were never enrolled e.g., subject screening log to address concerns over selection bias.

This trial will enroll a total of approximately 1,000 subjects; ~600 subjects ~200 per treatment arm) in the Efficacy Study part and ~400 subjects in the Safety Study part of the trial. Enrollment will stop when the minimum required number of subjects in each study group and study part is enrolled.

The number of completers after three months of treatment in the Efficacy Study part is anticipated to be around 435, anticipating a drop-out rate of 35% and 20% for non-hysterectomized and hysterectomized women, respectively. The number of completers after 12 months of treatment is anticipated to be ~300, anticipating a drop-out rate of 50% after one year of treatment.

The number of completers in Safety Study part after 12 months of treatment is expected to be ~200, anticipating a drop-out rate of 50%.

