12.7. Analysis of Secondary Efficacy Variables

All VMS related secondary efficacy variables will be analyzed using the same methodology as for the primary efficacy variables and will be based on the data from the ITT population.

All other secondary continuous efficacy variables will be analyzed using either an ANCOVA or an MMRM model depending on the type of endpoint considered. These models will be evaluated using data from the ITT, PP and mITT populations without imputation of data. Appropriate covariates may be included in the analyses.

The other categorical efficacy variables (scores, responder analysis) will be analyzed using appropriate statistical methods for the comparison of each treatment arm to the placebo arm.

In addition, all secondary efficacy variables will be tabulated at baseline and at each post-baseline time point.

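### The primary MMRM adds treatment-by-center when the center main effect is significant: the wrong trigger, and one that leaves the confirmatory model to the outcome data

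*Protocol*

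**What the plan says.** Protocol section 12.5 defines the primary MMRM with treatment, week, treatment-by-week and pooled center as fixed effects and baseline as covariate. It then adds: "If the pooled center effect included in the model is significant, a treatment by center interaction will be included in the model". The Synopsis repeats this. The rule stands in the definition of the primary model; center is not among the listed sensitivity analyses.

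The four co-primary endpoints are tested "using two separate MMRM models (one on weekly frequency and another on weekly mean severity". Section 12.4 scores severity two ways: "The analysis including the mild VMS will be used for submission to the FDA, the analysis without the mild VMS" for the EMA. That makes up to three primary fits. Section 12.7 extends the approach: "All VMS related secondary efficacy variables will be analyzed using the same methodology as for the primary efficacy variables".

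The protocol gives no significance level for the trigger, no pooling rule and no weighting of centers once the interaction is in the model.

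On hysterectomy status, section 7.2 says: "This assignment will take into account the modified MENQOL score, frequency and severity of hot flashes, hysterectomized vs. non-hysterectomized status". Section 7.3 names no stratification factor, only that "The computer program uses the method of randomly permuted blocks". Section 8.1 plans the 12-week completers "anticipating a drop-out rate of 35% and 20% for non-hysterectomized and hysterectomized women, respectively". Appendix 16.5.1 restricts Canadian sites to hysterectomized women. In section 12.5 the status appears only as a possible sensitivity analysis.

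**The concern.** The trigger tests one thing and is used to decide another. Centers can differ widely in mean change while the drug works equally well in all of them, and the reverse is also possible.

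The rule is written down in advance, but the model it yields is not. The center test uses the same outcome data as the treatment test, so the data choose the confirmatory model. The choice is made for each fit, so frequency and severity, or the FDA and EMA severity scores, can rest on different models although all four co-primaries must succeed together. Once the interaction is in, the treatment effect is an average over centers whose weights are not defined. Those weights change both what is estimated and how precisely.

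The hysterectomized-only Canadian sites add a second route: any outcome difference by hysterectomy status would partly appear as a center effect and could fire the trigger.

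**Working it through.** **Inputs from the protocol.** About 600 randomized 1:1:1, about 200 per arm, half hysterectomized; 12-week dropout 35% and 20%; two-sided 5%; Dunnett adjustment for two doses; power of at least 80%.

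**Inputs not in the documents, hence assumed.** 10 or 20 pooled centers; center intraclass correlation (ICC) 0-10%; trigger at p<0.05; largest-to-smallest center size 1, 3 or 10; within-subject correlation 0.7; correlation 0.5 between frequency and severity.

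**The plan's own figures.** Completers reproduce: 300 × 0.65 + 300 × 0.80 = 195 + 240 = 435, or 145 per arm. The 80% power does not, because no effect size, SD or correlation is given. Solving backwards for one endpoint, d = (1.960 + 0.842) × √(2/145) = 0.329.

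**Does the trigger detect an interaction?** Simulation with 435 subjects, one time point, 10, 20 or 30 centers and 1,500 trials per setting:
- Center SD 0.3, no interaction: trigger fires in 89-95% of trials; a direct interaction test is significant in about 4-6%.
- Interaction SD 0.5, no center main effect: trigger fires in 1-3%; a direct test is significant in 98-99.8%.

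**How often does it fire with no interaction?** For K equal centers of m = 600/K subjects, the variance of a subject's 12-week mean is 0.7 + 0.3/12 = 0.725. The center statistic is then about (1 + λ) times a chi-square on K−1 df, with λ = m × ICC / 0.725. For K = 20 and ICC 1%, λ = 30 × 0.01 / 0.725 = 0.414, and P(χ²₁₉ > 30.14/1.414) = 32%. A 12-week MMRM simulation with planned dropout (30 settings, 798-800 replicates each) agrees closely:

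| ICC | Trigger by formula, K = 10 / 20 | Trigger, simulated | Frequency and severity on different models, simulated |
|---|---|---|---|
| 0 | 5% / 5% | 4-6% | 8-10% |
| 1% | 41% / 32% | 29-39% | 36-40% |
| 3% | 85% / 82% | 79-84% | 25-30% |
| 5% | 95% / 96% | 92-96% | 7-14% |
| 10% | 99% / 100% | 99-100% | 0-2% |

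**Type I error, no true interaction.** 3.6-6.2% with the rule and 3.7-6.2% without it (nominal 5%).

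**Precision once the interaction is in.** With equal center weights, the SE relative to the additive model is about √(mean of n × mean of 1/n) over center sizes n. It is 1 for equal sizes. For ten evenly spaced sizes from 1 to 3 it is √(2 × 0.5627) = 1.06; from 1 to 10 it is √(5.5 × 0.2929) = 1.27. The simulated MMRM gave +0.0-0.1%, +4% and +19-22% for ratios 1, 3 and 10. With size weights it gave +0.0-0.2% throughout.

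**Power for one dose and one endpoint.** With the Dunnett critical value 2.212, 80% power needs an effect of 2.212 + 0.842 = 3.054 standard errors. At SE × 1.22, power is Φ(3.054/1.22 − 2.212) = Φ(0.291) = 61%. Simulated power without the interaction was 77.6-82.6%. The lowest under the rule with equal weights was 77.9%, 75.5% and 60.1% for ratios 1, 3 and 10: losses of none, 0-4 and 1-21 points. With size weights the loss was at most 0.7 points.

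**Hysterectomy mix alone.** With 10-30% of centers hysterectomized-only, a 0.2-0.4 SD outcome difference and no other center effect (all assumed; 12 settings, 300 replicates each), the trigger fired in 5-73% of fits.

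**The case against.** The strongest reply is that the governing document has not been seen. The supplied SAP covers only the Safety Study part and marks treatment-by-center as not applicable; it cites an Efficacy Study Part SAP v3.0 of 05Apr2022. Trigger level, pooling and weighting normally belong there. This stands as a limit: the finding concerns the protocol text. Protocol v8.0 (June 21, 2022) is later and keeps the rule, but Amendment 7 lists no change to section 12, so its silence says nothing about the Efficacy SAP. If that SAP replaced the rule, the two documents still need to be reconciled.

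Second, the harm is conditional. Type I error is not inflated, and the 21-point loss needs the trigger to fire, 10:1 sizes and equal weights together. Pooling may reduce the imbalance. This also stands, and it limits the size of the problem. It does not make a center main effect a test of interaction.

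Third, frequency and severity already have separate models, and nothing requires their terms to match. That is fair as far as it goes: no inferential error from the mismatch itself was shown. The cost is a confirmatory analysis that cannot be fully stated beforehand.

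Fourth, the case for hysterectomy status is weaker. Section 7.2 also covers allocation to study parts and does not establish stratified randomization. Dropout that differs by status alone does not bias the treatment contrast, and the status's prognostic value is not given. These points are right, and the conclusion does not depend on it.

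**Conclusion.** The rule is wrong as written. It uses a center main effect to decide on a treatment-by-center term, and it lets the outcome data choose the confirmatory model for each co-primary fit. The mismatch between trigger and purpose follows from the definitions; the simulations only show its extent.

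The practical size ranges from negligible (equal-sized centers or size weights) to a power loss of up to 21 points (10:1 sizes with equal weights). Which case applies cannot be settled from the protocol. All rates rest on assumed center numbers, sizes, ICC and trigger level, and power was calibrated to one dose and one endpoint, not to all four co-primaries. This should be corrected. Confidence is medium, mainly because the Efficacy SAP was not available.

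**What to change.** In section 12.5 and the Synopsis, delete the conditional sentence. State that every primary fit uses treatment, week, treatment-by-week, pooled center and hysterectomy status as fixed effects and baseline as covariate, whatever the significance of the center effect. State the pooling rule. Report treatment-by-center as a pre-specified supportive analysis with its own test and its center weighting stated. Bring the Efficacy Study Part SAP into line, or confirm that it already replaces the rule.

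Hysterectomy status is the optional part. It supports the missing-at-random assumption, given the planned dropout difference; any gain in precision depends on its prognostic value.

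The cost is wording in two protocol places through a formal amendment (section 13.5), alignment of the SAP, and one degree of freedom for a variable already collected. No new data are needed. The change must precede unblinding for the Visit 4 efficacy analysis (section 12.9). The documents do not show whether that analysis is still ahead; if it has been run, the revised model would be post hoc and should be labeled so.
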